6. ANALYSIS POPULATIONS

For the primary and secondary outcomes, consistent with the recent JAMA Guide to Statistics and Medicine ([Detry, 2014](#)), all analyses will be performed consistent with the intent-to-treat (ITT) principle, meaning all study participants will be analyzed as-randomized.

The proportion of randomized study participants completing each visit will be summarized as in Table 1 below.

Table 1: Completeness of Study Data by Visit

Visit	Placebo (N = XX)	120 mg (N = XX)	160 mg (N = XX)
0	XX (XX%)	XX (XX%)	XX (XX%)
2	XX (XX%)	XX (XX%)	XX (XX%)
4	XX (XX%)	XX (XX%)	XX (XX%)
6	XX (XX%)	XX (XX%)	XX (XX%)
8	XX (XX%)	XX (XX%)	XX (XX%)
10	XX (XX%)	XX (XX%)	XX (XX%)
12	XX (XX%)	XX (XX%)	XX (XX%)

7. PRIMARY ANALYSIS

Primary Objective: *The primary objective is to evaluate the tolerability of SRX246.*

The first primary objective of this study is to evaluate the tolerability of SRX246 versus placebo. The Go/No-Go decision for further consideration of SRX246 will be based on testing tolerance among the placebo and treatment groups using a single-tailed test. Because this is an early-phase study (phase IIa), the primary objective will be met by conducting a non-inferiority test ([Blackwelder, 1982](#)) of the proportion of study participants who complete the study while active on their assigned intervention arm among the placebo group and each of the treatment groups. Separate tests will be conducted for each of the treatment arms (i.e., a separate test for placebo vs. 120 mg and placebo vs. 160 mg) with a significance level of 0.025 for each test in order to apply an alpha-correction to control for multiple comparisons.

In traditional comparative analysis, the typical null hypothesis (H_0) states that two groups have equal values for their respective parameters, such as the means of the groups. That is, H_0 states that there is no difference between the parameters of the groups. The alternative hypothesis (H_A) states that the two groups are unequal regarding the parameter (i.e., the difference between the parameters is not 0). Failure to reject H_0 means we cannot rule out equal group parameters, and rejection of H_0 indicates the parameters might be unequal.

Non-inferiority test differs from the traditional analysis in that H_0 states that the difference between the parameters of the groups is equal to or greater than a threshold value, δ , which is a meaningful cutoff value that is usually based on clinical relevance or previous research results. Conversely, H_A states that the difference is less than δ . The test of non-inferiority is inherently one-tailed, as H_0 and H_A are directional hypotheses. Focus is on the difference in the proportion of participants meeting the study definition for tolerability in each group. Let us denote the population proportion of study participants meeting the study definition for tolerability in the placebo group as π_{placebo} , and the population proportion of participants meeting the study definition for tolerability in the 120 mg group as $\pi_{120\text{mg}}$ (a similar proportion is defined for the 160 mg group). Consider the non-inferiority hypotheses for the comparison of the placebo and 120 mg groups:

$$H_0: \pi_{\text{placebo}} - \pi_{120\text{mg}} \geq \delta$$

vs.

$$H_A: \pi_{\text{placebo}} - \pi_{120\text{mg}} < \delta.$$

For the purposes of this study, the non-inferiority margin was set to $\delta = 0.5$, which is the same value used in a series of clinical trials sponsored by the Huntington Study Group ([HSG, 1998](#); [HSG, 2003](#); [HSG, 2004](#); [HSG/TETRA-HD Investigators, 2009](#)). Using this threshold means that when H_0 is rejected, $\pi_{120\text{mg}} - \pi_{\text{placebo}} < 0.5$. Or, equivalently, the tolerability in the treated group is less than 50% lower than the tolerability in the placebo group, which is taken to be a negligible (non-meaningful) difference in tolerability. Thus, non-inferiority of tolerability within the margin is consistent with the rejection of the null hypothesis and will constitute a Go decision for further consideration of that dose of SRX246, perhaps in a phase IIb study to detect signs of activity. Conversely, failure to reject the null hypothesis would imply that there could be tolerability concerns and will result in a No-Go decision for that dose. Note that rejection of H_0 does not necessarily mean there is strict equivalence among the groups (i.e., does not imply that the difference is 0). Rather, any tolerability difference is below the acceptable 50% threshold.

The statistical test of H_0 will be performed using a one-sided CI for the difference of the proportions based on exact methods. Exact methods have known sampling distributions in contrast to asymptotic methods that have approximate sampling distributions ([Agresti, 2003](#)). Exact methods are preferable because their confidence intervals (CIs) have a minimum coverage probability, especially for small sample sizes (the minimum is $1 - \alpha$). The CI to be used corresponds to inverting a family of exact tests, with the 97.5% CI ($\alpha = 0.025$) including all the values that are not rejected at the .025 level in the corresponding test. Though an exact CI has a minimum coverage probability of $1 - \alpha$, its length can be too long, which means the associated inverted test has low statistical power. To address this issue, and to ensure that H_0 is evaluated using the highest possible statistical power, a computer-intensive method will be used to select the shortest one-sided CI for testing ([Wang, 2010](#)).

The exact testing assumes binomial distributions for the variables. A study participant is classified as meeting the definition for tolerability if they complete the study on assigned treatment, or as a non-completer if they do not finish the trial (withdrawal for any reason) or have to withdraw from assigned treatment before the end of the study. The number of participants meeting this definition in the placebo group and each treatment group (e.g., 120 mg) is binomially distributed. There is an analytic formula for the joint probability function, which forms the basis of the exact test.

Suppose that $\theta = \pi_{\text{placebo}} - \pi_{120\text{mg}}$, so that $H_0: \theta \geq 0.5$ and $H_A: \theta < 0.5$. We reject H_0 if the one-tailed $1 - \alpha$ CI for θ does not contain 0.5. When the proportions are equal, $\theta = 0$, and when tolerability is higher in the placebo group, $\theta > 0$. Therefore, we are interested in the lower one-sided CI with range $[-1, \text{UCI}]$, where UCI is the upper CI limit. If $\text{UCI} < 0.5$, then we reject H_0 . If $\text{UCI} \geq 0.5$, then we do not reject H_0 . In summary,

$$\text{UCI} < 0.5, \quad \text{Reject } H_0;$$

$$\text{UCI} \geq 0.5, \quad \text{Do Not Reject } H_0.$$

For each analysis, we set $\alpha = 0.025$, which means H_0 is tested with a one-sided $1 - \alpha = 0.975$ CI.

An additional consideration is that using the usual asymptotic test can be inaccurate with smaller sample sizes, especially when π_{placebo} (or $\pi_{120\text{mg}}$) are close to 1.0, as is anticipated in this study ([Fagerland, 2011](#)). Computer intensive exact methods can have better performance under these conditions ([Santner, 2007](#)). The shortest lower one-sided CI will be computed with a computer-intensive ranking-based method ([Wang, 2010](#)). Wang's method appears to have superior performance to other approaches, and software is readily available ([Wang, 2012](#)).

The method will be computed with the `BinomCI()` function of the `ExactCI` package ([Shan & Wang, 2013](#)) for the R computing software.

The results of the tolerability analysis will be summarized graphically, with a bar plot showing the proportion difference and one-sided CI for each group comparison. The results will also be depicted as in [Table 2](#) below.

Table 2. Proportion of Participants Meeting Study Definition for Tolerability

Group	Placebo (N = XX)	120 mg (N = XX)	160 mg (N = XX)
Number (%)	XX (XX%)	XX (XX%)	XX (XX%)
One-Sided CI for Difference	N/A	[-1 , XX%]	[-1 , XX%]
Decision	N/A	Tolerable (Yes/No?)	Tolerable (Yes/No?)

8. SECONDARY ANALYSIS

Secondary Objective: *The secondary objective is to evaluate the safety of SRX246.*

The safety objective will be met by conducting a non-inferiority test of the proportion of study participants with AEs or SAEs among the placebo group and each of the treatment groups (separate tests for placebo vs 120 mg and placebo vs 160 mg). The safety analysis will be conducted in a similar manner as the tolerability analysis. Each study participant will be classified as having experienced a treatment-emergent AE or SAE (event = "Yes") or not (event = "No"). Suppose the proportion of events in the placebo group is now denoted as π_{placebo} and the proportion of events in the 120 mg group is now $\pi_{120\text{mg}}$, with $\theta = \pi_{\text{placebo}} - \pi_{120\text{mg}}$. The same onesided CI will be used to test the same null hypothesis ($H_0: \theta \geq \delta$) with the same threshold ($\delta = 0.5$) as in the tolerability analysis. Each treatment group (120 mg, 160 mg) will be compared to the placebo group using $\alpha = 0.025$, meaning a $1 - \alpha = 0.975$ one-sided CI will be used for each test. Results will be summarized as shown in Table 3 below.

Table 3. Summary of Safety Analyses

	Placebo (N = XX)	120 mg (N = XX)	160 mg (N = XX)
Any AE	XX (XX%)	XX (XX%)	XX (XX%)
Any Treatment-Related AE	XX (XX%)	XX (XX%)	XX (XX%)
Any Serious AE	XX (XX%)	XX (XX%)	XX (XX%)
Early Drug Withdrawals (Any)	XX (XX%)	XX (XX%)	XX (XX%)
Early Drug Withdrawals (Due to AE)	XX (XX%)	XX (XX%)	XX (XX%)
Early Terminations (Any)	XX (XX%)	XX (XX%)	XX (XX%)
Early Terminations (Due to AE)	XX (XX%)	XX (XX%)	XX (XX%)
Deaths (Any)	XX (XX%)	XX (XX%)	XX (XX%)
Deaths (Due to AE)	XX (XX%)	XX (XX%)	XX (XX%)

In addition to an overall comparison, this hypothesis will be repeated for assessing the percentage of study participants having at least one treatment-emergent AE within each MedDRA system organ class (SOC). If there are specific differences within any specific SOC, then additional tests will compare differences across groups for specific MedDRA preferred terms in order to further explore the cause of the observed differences. Finally, the subset of treatment-related SAEs will be analyzed in the same manner described above.

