6.12 Dosage Adjustments

Dosage adjustments (dose reductions and suspensions) will be allowed if warranted, in the clinical judgment of the site Investigator in consultation with the medical monitor. Restarting study drug after suspensions will be allowed. The overall goal is to encourage each Subject to reach the target dosage and complete the study. The CTCAE Version 4.0 may be used as a reference guide for dosage adjustments. Grade 2 or greater adverse effects for laboratory values and clinical events should be considered when evaluating tolerability and determining whether a dose reduction is warranted. While these criteria will be used as a guide, site investigators, in consultation with the medical monitor, will ultimately make the decisions about dosage adjustments.

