An additional consideration is that using the asymptotic test with our estimated sample size might not be optimal. The asymptotic test can be inaccurate with smaller sample sizes, especially when π_P (or π_T) is close to 1, as is anticipated in the proposed study (cf Table 4) (Fagerland 2011). Computer-intensive exact methods can have better performance under these conditions (Santner 2007). The exact method discussed by Wang (2010) will be used for the proposed analysis of tolerability and safety (the latter is discussed below). Wang's method appears to have superior performance to other approaches, and software is readily available (Wang 2013).

Secondary Aim: Safety. The secondary aim of the analysis is safety, with the endpoint defined as the proportion of participants who experience an adverse event (AE). A non-inferiority analysis for safety will be performed, similar to that discussed for tolerability. Primary focus will be on the comparison of 160mg vs placebo. H_0 for non-inferiority will be evaluated using the methods previously described with the same margin of difference, $\delta = 0.50$.

Consistent with the recent JAMA Guide to Statistics and Medicine (Detry 2014) the analysis will be performed consistent with the intent-to-treat principle, meaning an attempt will be made to analyze all enrolled patients. Missing data methods, such as imputation, might be used to handle dropout (note this is not an issue for the tolerability analysis as the proportion of completers is the endpoint).

Exploratory Aim: Activity of Measures. The exploratory aim is to examine several measures of irritability and other problem behaviors and clinical assessment for activity signal. Measures will be compared to each other and also compared to clinical assessments in order to examine relative

effect sizes. The endpoint will be rate of change (slope) over 12 weeks. Linear mixed models (LMMs) (Verbeke 2000) will be used to examine slope differences among the placebo and treatment groups. LMMs are appropriate for the analysis because they account for dependency due to repeated measures and can be estimated with maximum likelihood (ML) procedures.

Consistent with the intent-to-treat principle, ML estimation can accommodate missing data under the assumption that the missing data mechanism is ignorable (Little 1987).

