10.3.1 Assessment of Adverse Events

At each visit (including telephone interviews), the Subject will be asked "Have you had any problems or symptoms since your last visit?" in order to determine the occurrence of adverse events. If the Subject reports an adverse event, the Investigator will determine:

1. Type of event
2. Date of onset and resolution (duration)
3. Severity (mild, moderate, severe)
4. Seriousness (does the event meet the above definition for an SAE)
5. Causality, relation to investigational product and disease
6. Action taken regarding investigational product
7. Outcome

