3. SECONDARY ENDPOINT

The secondary endpoint for safety is defined as the proportion of study participants who experience any treatment-emergent (starting at or after the first dose of study medication) adverse event (AE) or serious adverse event (SAE). For the purposes of this study, a treatment emergent adverse event (AE) is any untoward medical occurrence associated with the use of a drug in humans, whether or not considered drug related. FDA, Office of Human Research Protection (OHRP) and NeuroNEXT CIRB requirements for reporting AEs will be followed. AEs are generally detected in two ways:

- Clinical → Symptoms reported by the study participant or signs detected on examination
- Ancillary Tests → Abnormalities of vital signs, laboratory tests, and other diagnostic procedures

If discernible at the time of completing the AE source documentation, a specific disease or syndrome rather than individual associated signs and symptoms should be identified by the Site Investigator and recorded in the AE documentation. However, if an observed or reported sign, symptom, or clinically significant laboratory anomaly is not considered by the Site Investigator to be a component of a specific disease or syndrome, then it should be recorded as a separate AE in the source documentation. Clinically significant laboratory abnormalities, such as those that require intervention, are identified as such by the Site Investigator.

Each clinical study site's Principal Investigator and research team (co-investigators, research nurse, and clinical trial coordinator) are responsible for identifying and reporting AEs through the NeuroNEXT Online Adverse Event Reporting System. The AE definitions and reporting procedures used for this study comply with all applicable U. S. Food and Drug Administration (FDA) regulations and International Conference on Harmonization (ICH) guidelines. The Site Investigator will carefully monitor each study participant throughout the study for possible AEs. All AEs will be documented on CRFs designed specifically for this purpose. It is important to report all AEs, especially those that result in permanent discontinuation of the investigational product, whether serious or non-serious. Local site investigators are also required to fulfill all reporting requirements of their local institutions.

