Study participants who sign consent and receive investigational treatment will be monitored for AEs from the time they sign consent through week 12 or the end of their study participation. This study utilized the CTCAE version 4.03 coding system for AE recording. AEs reported using CTCAE will be recoded into MedDRA terms by the DCC.

At each visit, the participant will be asked "Have you had any problems or symptoms since your last visit?" in order to determine the occurrence of AEs. If the study participant reports an AE, the Investigator will determine:

- Type of event
- Date of onset and resolution (duration)
- Severity (mild, moderate, severe, life-threatening, results in death)
- Seriousness (does the AE meet the definition of an SAE)
- Causality, relation to investigational product and disease
- Action taken regarding investigational product
- Outcome

All clinical AEs are recorded in the AE data entry template in the study participant's study binder. The sites should fill out the AE data entry template and enter the information into the Online Adverse Event Reporting System (AERS) within 5 working days / 7 calendar days of the site learning of a new AE or receiving an update on an existing AE. Entries in the AE data entry template will include the following:

- Name and severity of the AE
- Date of onset
- Date of resolution

- Relationship to study drug
- Action taken
- Primary outcome of event

The severity of all AEs will be graded according to CTCAE, version 4.03. Any AE not listed in the CTCAE will be graded as follows:

- Grade 1 – Mild: Transient or mild discomfort; No limitation in activity; No medical intervention/therapy required
- Grade 2 – Moderate: Mild to moderate limitation in activity; Some assistance may be needed; No or minimal medical intervention/therapy required
- Grade 3 – Severe: Marked limitation in activity, some assistance usually required; Medical intervention/therapy required; Hospitalizations possible
- Grade 4 – Potentially Life-Threatening: Extreme limitation in activity; Significant assistance required; Significant medical intervention/therapy required; Hospitalization or hospice care probable
- Grade 5 – Death: The AE results in death

The Site Investigator is initially responsible for classifying AEs as serious or non-serious. An AE is considered serious if it meets one or more of the following criteria:

- Results in death

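### No planned by-arm safety output uses the CTCAE grade recorded for every adverse event, so a rise in higher-grade, non-serious events that neither stop nor lastingly lower treatment would not be seen

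*SAP*

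**What the plan says.** SAP section 3 sets the secondary endpoint, "defined as the proportion of study participants who experience any treatment-emergent (starting at or after the first dose of study medication) adverse event" or SAE. Protocol 8.1.2 and 8.2 define the same kind of endpoint, without a grade. SAP section 8 turns it into a Yes/No per participant ("Each study participant will be classified as having experienced a treatment-emergent AE or SAE") and compares each dose with placebo.

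SAP section 3 also states: "The severity of all AEs will be graded according to CTCAE, version 4.03". It lists five levels, from mild to death.

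Table 3 in SAP section 8 has nine rows by arm: any AE, any treatment-related AE, "Any Serious AE", and early drug withdrawals, early terminations and deaths (each overall and due to AE). Section 8 then repeats the test within each MedDRA system organ class, goes down to preferred terms where classes differ, and tests treatment-related SAEs. None of these uses grade.

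Three other places bear on severity:
- Protocol 6.12, on dose adjustment, says that "Grade 2 or greater adverse effects for laboratory values and clinical events should be considered when evaluating tolerability".
- Protocol section 7 gives a general strategy by grade. A Grade 2 event leads to a hold and then the same dose level, a Grade 3 event to a hold and then one level lower, and a Grade 4 event to the end of therapy.
- SAP section 2 counts as a non-completer anyone who withdraws from study drug or finishes below the assigned dose. Temporary interruptions do not prevent completion.

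**The concern.** A participant with a single Grade 1 event and a participant with a Grade 2 event that interfered with usual activities both score Yes. If the drug moves events from mild to moderate without changing how many participants have at least one, the main comparison does not move. The grade that would show the shift is entered for every event but is left out of the final by-arm analysis.

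The endpoint may also have little room to move. AEs are asked about at seven contacts after baseline (weeks 2, 4, 6, 8, 10 and 12, and the follow-up call). Worsening of a chronic condition counts as an AE (Protocol 10.1), and Protocol section 7 expects behavioral symptoms as AEs because of HD itself. A high any-AE rate in all arms is plausible, though not documented.

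At stake is what a tolerability and safety trial can say about two doses in a population that, by Protocol section 8, may be frailer than those given the drug before.

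**Working it through.** **1. The plan's own figure.** The documents give no power or sample size for the safety endpoint. The stated size comes from tolerability: placebo 0.80, drug 0.60, margin 0.50, one-sided 0.025, 80% power. With the standard formula, n = (1.960 + 0.842)² × (0.80×0.20 + 0.60×0.40) / (0.50 − 0.20)² = 34.9, so 35 per arm. Protocol 8.2 has 35 in its power text and SAP section 9 has 36. I use 36.

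**2. Where each kind of event appears by arm.**

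| Participant's worst event | Table 3 rows | Primary endpoint |
|---|---|---|
| Grade 1, non-serious | Any AE (and treatment-related, if so judged) | Completer |
| Grade 2, non-serious, held once, resumed at same dose | Same rows as above | Completer (interruption allowed) |
| Grade 3, non-serious, dose unchanged | Same rows as above | Completer |
| Grade 3, finishes below assigned dose | Same rows as above | Non-completer, not separated by cause |
| AE leading to drug withdrawal | Adds the withdrawal rows | Non-completer |
| Serious AE | Adds the serious AE row | Depends on drug and dose |

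The first three lines cannot be told apart in the planned by-arm output. Table 3 has no row for dose reduction.

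**3. What the any-AE test does when only severity shifts.** Hold the any-AE rate equal in both arms and enumerate all outcomes at 36 per arm. A score test stands in for the planned exact interval. The safety test passes 99.4%, 99.8%, 99.97% and about 100% of the time at assumed rates of 50%, 70%, 80% and 90%. Grade does not enter the calculation, so these figures hold for any mix of grades.

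**4. Room for any AE to rise.** If a share p of placebo participants have an AE, the largest possible excess on drug is 1 − p: 50, 30, 20 and 10 points at p = 0.50, 0.70, 0.80 and 0.90. All values of p are assumptions.

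**5. Illustration (assumed rates, 36 per arm).**
- Any AE 80% on placebo, 85% on drug: SE = √((0.16 + 0.1275)/36) = 0.089. The difference is 0.05, and 0.05/0.089 = 0.56 SE.
- Grade 2 or above 30% on placebo, 60% on drug: SE = √((0.21 + 0.24)/36) = 0.112. The difference is 0.30, or 2.68 SE, with 95% CI 0.30 ± 1.96 × 0.112, about 8 to 52 points.

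**6. Why the planned interval should not be reused.** Section 8 sets θ = placebo minus drug and passes if the upper limit is below 0.50. At 30% on placebo and 60% on drug, the upper limit is −0.30 + 1.96 × 0.112 = −0.08, which passes easily. More generally, if the observed rate on drug is at or above placebo, θ is estimated at 0 or less. The upper limit is then at most about 1.96 × √(0.50/36) = 0.23, well under 0.50. Enumeration with the score test agrees: at 20% on placebo and 90% on drug, the test passes with probability 1.00.

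**7. Precision of a Grade 3 or above row.** For one-sided 0.025 tests at assumed rates (placebo, drug), power is 49% at 5%, 20%; 57% at 10%, 30%; 81% at 5%, 30%; and 85% at 10%, 40%. The 95% CI half-widths are about 15 to 19 points. That is enough for a descriptive estimate, but not for a confirmatory claim.

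**The case against.** The strongest reply is that severity is already represented. Table 3 shows by arm serious AEs, withdrawals and terminations due to AE, and deaths. Treatment-related SAEs get their own test, and there are system-organ-class and preferred-term tests. Under Protocol section 7, Grade 3 and 4 events tend to lead to a lower dose or the end of therapy, as does a hold beyond one week or a second hold. SAP section 2 counts those outcomes as non-completion.

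Most of this stands, and it rules out some readings that a reader might reach for:
- That a drug which worsens AEs would look identical to placebo. This is true only of the any-AE test.
- That the any-AE test is the only formal safety comparison. Section 8 has others.
- That Protocol 6.12 makes Grade 2 an analysis threshold. It guides individual dose decisions, and investigators decide.
- That any AE is known to sit near its ceiling. The documents give no rate.
- That sites graded on different scales. Protocol 10.3.1 names three severity levels, but Protocol 10.3 adopts CTCAE 4.0 and section 7 uses Grades 1 to 4, so the short list is probably shorthand.

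The reply leaves a remainder. Section 7 is a general strategy in which relatedness is weighed, so a Grade 3 event need not change the dose. Grade 2 events resume at the same dose. Dose reductions enter only a non-completer count that mixes all causes. The severity summaries in Protocol 9.8 and SAP 10.1 are blinded aggregates for monitoring, not a by-arm analysis.

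**Conclusion.** The gap is real and limited. The main safety comparison ignores grade, and no planned by-arm safety output uses it. What goes unseen is a rise in higher-grade, non-serious AEs that cause no withdrawal and no lasting dose reduction. Grade 2 events held and resumed at the same dose are the clearest case. This follows from the documents and needs no assumed rate.

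The size does rest on assumptions. The 30-point shift in Grade 2 or above beside a 5-point shift in any AE shows what could be missed; it is not a forecast.

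Nor should a reader infer that the present test would at least detect AEs that become more frequent on drug. With θ as placebo minus drug and a 0.50 margin, it would not. That is a separate fault, raised here because it decides how the added rows should be analyzed.

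**What to change.** Add to SAP section 8 and Table 3, by arm, the number and percentage of participants whose maximum treatment-emergent CTCAE grade is 2 or above, and 3 or above. For each dose, give the drug-minus-placebo difference with a two-sided 95% CI, labelled supportive. Do not apply the planned placebo-minus-drug interval or the 0.50 margin to these rows.

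State in the SAP that the five-level CTCAE 4.03 grade is the analysis scale. The SAP describes randomization in the past tense, so this belongs in the SAP, not in an edit to Protocol 10.3.1. The words adding SAEs to the any-AE endpoint are redundant and could go; the separate serious AE row should stay.

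The cost is a few lines of SAP text and two table rows, from data already entered for every AE. The downside is one more supportive secondary comparison, with wide intervals at 36 per arm. The addition should be dated before database lock and unblinding; otherwise it should be reported as post hoc.
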